9.7.2 Preparation and labeling

Venetoclax is available in tablets of 10, 50 or 100 mg.

Venetoclax will be shipped to trial sites labeled as an Investigational Medicinal Product. Venetoclax will be prepared and labeled in compliance with GMP and other applicable regulatory requirements.

9.7.3 Storage and handling

Venetoclax should be stored and handled in accordance with the instructions in the Investigator's Brochure. The investigational medicinal product should be stored in such a manner that accidental loss or destruction or access by an unauthorized person is prevented.

9.7.4 Study drug supply

The sponsor will arrange delivery of venetoclax to trial sites. No investigational medicinal product will be shipped until the sponsor has verified that all regulatory required documents and approvals for the site are available. Venetoclax will be dispensed to subjects in blister packs through the dose ramp up period, and in bottles at each subsequent visit.

9.7.5 Drug accountability

The investigator, or a pharmacist or other appropriate individual who is designated by the investigator, should maintain records of the product's delivery to the trial site, the inventory at the site, the use by each patient, and the return to the sponsor or alternative disposition of unused product(s). These records should include dates, quantities, batch/serial numbers, expiration dates (if applicable), and the unique code numbers assigned to the investigational product(s) and trial patients (if applicable). Investigators should maintain records that document adequately that the patients were provided the doses specified by the protocol and reconcile all investigational product(s) received from the sponsor. The investigator should also collect and count remaining medication, empty boxes and blisters of medication to check that the patient has taken the assigned dose.

9.7.6 Study drug return and destruction

Partially used investigational medicinal product should not be redispensed to either the same or another patient after it has been returned.

The trial site should destroy used or partially used study drug containers after drug accountability records have been completed. Destruction should be documented.

At the end of the trial or after expiry of the product unused investigational medicinal product should be returned to AbbVie

10 Study procedures

10.1 Time of clinical evaluations

- Before enrollment: within 28 days before registration, as specified in 10.2
- After each cycle until end of cycle 15
- Weekly during venetoclax ramp up in cycle 3
- After cycle 15: every 3 months for 2 years and every 4 months for the 3rd year, whether in the maintenance or the treatment cessation group, until month 51 (15 months + 3 years)
- Thereafter every 6 months until 7 years after registration or until progression, whatever comes first.

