Patients randomized to arm B who become MRD positive or have symptomatic CLL according to IWCLL criteria during the observation period reinitiate treatment with both ibrutinib and venetoclax for 12 cycles and continue ibrutinib treatment until toxicity or progression.

Only patients randomized for observation (arm B) are considered for the primary endpoint without formal comparison between arms.

Duration of treatment

All patients receive ibrutinib + venetoclax (with delayed start

and ramp up of venetoclax from cycle 3) for the first 15 cycles.

Thereafter Ibrutinib maintenance until progression/toxicity or observation without treatment.

Patients randomized to arm B who become MRD positive or have symptomatic CLL according to IWCLL criteria during the observation period reinitiate treatment ibrutinib + venetoclax for 12 months and continue ibrutinib treatment until toxicity or progression.

Subsequently all patients will be followed until 7 years after registration

Target number of patients	207 eligible patients. In order to take into account possible dropout due to ineligibility, 230 patients will be registered
Expected duration of accrual	Expected start of recruitment Q2/2017 Expected end of recruitment Q2/2020
Main study endpoints	
Primary endpoints: (Only considered for arm B of the study)
 
 - Proportion of patients fulfilling the criteria for progression free survival (PFS) at 12 months after stopping therapy (27 months after starting treatment) for patients randomized to stop treatment , reinitiated treatment due to MRD positivity not considered progression (see section 13.1 for details). 
Secondary endpoints (for all treatment groups):
 
 - Minimal residual disease (MRD) at 12 months after stopping treatment (month 27) for patients randomized to stop treatment, - PFS (IWCLL criteria), - Time to and number of patients reinitiating treatment, - Time to treatment failure after reinitiated treatment, - Time to next CLL treatment, - MRD after cycle 12 (PB), day 15 cycle 15 (PB and

- BM) and at later time points in PB,
- Overall survival (OS),
- Complete response (CR)/ Partial Response (PR)/ Stable disease (SD) after cycle 3, 9, 12, 15 and month 27 and 51 (3 years after stopping treatment),
- Duration of response,
- Safety parameters: Type, frequency, and severity of
 - o adverse events (AEs) and

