10.1.1 Follow up

All patients will be followed until 7 years after registration.

To be able to collect long term follow up data until patient`s death after the end of this study, inclusion in a country specific registry (e.g. the Danish National CLL register or the Dutch Pharos registry or registry of the other Nordic countries) is strongly recommended. For this purpose, each patient will be informed about the importance of long term follow-up data and asked for his/her consent to the long term follow-up within an appropriate registry. For patients with a written informed consent for the registry, data for overall survival, late toxicities such as secondary malignancies, further treatments and the course of the disease will be collected after the end of the trial.

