10.2 Required investigations

Table 10.2.1 Required investigations at entry, during treatment and during follow up

	At entry ¹	After each induction cycle	Extra at end of cycle 2	Cycle 3 day 8 and 15 Cycle 4 day1	Extra at end of cycle 3 and 6	Extra at end of cycle 9	Extra at end of cycle 12	Extra at day 15 of cycle 15 ⁹	After cycle 15: Every 3 months for 2 years, every 4 months for 3 rd year (= until 51 months)	Extra at month 27	After month 51 ²	Progressive disease
Informed consent	X											
Medical history	X											
Adverse events	X	X							X		X	
Physical examination	X	X							X		X	X
CIRS / CCI	X											
Rapid Report Form					X	X	X					
Binet stage	X											
TLS risk category (appendix G)	X		X ⁴									
Lab tests												
Hematology	X	X							X		X	X
Blood chemistry	X	X							X		X	
Additional chemistry	X											
Virology	X											
Bone marrow												
Bone marrow biopsy								X		X		X
(PET)-CT scan ⁵	X		X ⁶					X		X		X
(Clinical) response evaluation					X ⁷	X	X		X	X	X	X
Quality of Life ⁷	X								X ⁸		X ⁸	
Pregnancy test	X											

- Laboratory tests should be performed within 2 weeks prior to registration flow and CT can be maximally 42 days old
- Every 6 months until 7 years after registration or until progression, whatever comes first.
- The form needs to be filled out every 3 months for as long as the patient is on ibrutinib treatment
- In patients with high risk for TLS or CrCL 30-50 ml/min
- PET only in case of suspected transformation.
- CT scan after cycle 2 in patients with high risk for TLS or CrCL 30-50 ml/min
- Only at end of cycle 3
- Quality of life at entry, after induction cycle 15 and at 6 months, 1, 2 and 3 years after start maintenance/observation.

9. MRD and CT should be done at day 15 cycle 15 to have results available to assess SD, PR, CR, MRD negativity at end of cycle 15.

Table 10.2.2 .Collection for central lab.

	At entry	After each induction cycle	Extra at end of cycle 2	Cycle 3 day 8 and 15 Cycle 4 day1	Extra at end of cycle 3 and 6	Extra at end of cycle 9	Extra at end of cycle 12	Extra at day 15 of cycle 15 ⁴	After cycle 15: Every 3 months for 2 years, every 4 months for 3 rd year (= until 51 months)	Extra at month 27	After month 51	Progressive disease
Mutational status¹ PB	X											
Serum parameters	X											
FISH/CGH and NGS PB	X											X
MRD (flowcytometry)												
PB	X		X			X	X	X	X ²	X ²		X
BM aspirate								X		X		X
Side studies												
PB	X		X	X		X	X	X	X	X		X

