BM aspirate								X		X		X
Lymph node biopsy												X ³

1 If not performed earlier

2 Patients becoming MRD pos. retest 1 month later (only during observation)

3 If accessible lymph node is present

4. MRD and CT should be done at day 15 cycle 15 to have results available to assess SD, PR, CR, MRD neg at end of cycle 15.

Table 10.2.3 Required investigations during/after reinitiation treatment¹

	Before start of reinduction treatment	Extra at end of cycle 3	Extra at end of cycle 12	After cycle 12: Every 3 months for 2 years, every 4 months for 3 rd year	Extra at 1 year after cycle 12	After month 51 ²	Progressive disease
Medical history	X			X		X	
Adverse events	X			X		X	
Physical examination	X			X		X	X
TLS risk category (appendix G)	X						
Lab tests							
Hematology	X			X		X	X
Blood chemistry	X			X		X	
Additional chemistry	X						
Bone marrow							
Bone marrow biopsy			X		X		
(PET)-CT scan	X		X		X		X
(Clinical) response evaluation		X	X		X	X	X
Quality of Life²	X						
CENTRAL LAB							
Flowcytometry PB (or BM if PB not done)							X
FISH/CGH and NGS PB							X
MRD (flowcytometry)							
PB			X	X	X		X
BM aspirate			X		X		X
Side studies							
PB			X		X		X
BM aspirate			X		X		X
Lymph node biopsy							X ³

1 Note that the required investigations from month 27 as mentioned in table 10.2.1 are required for all patients

2. Follow the original schedule: quality of life at 1, 2 and 3 years after start maintenance/observation

3. If accessible lymph node is present

Medical history

Standard medical history, including:

- B symptoms
- Concomitant diseases
- Concomitant medications
- Adverse events

At entry

- Proven CLL or SLL by minimal required markers (CD19/CD20/CD5/CD23/Kappa/Lambda)
- Cumulative Illness Rating Score (see appendix F)
- Binet classification (see appendix A)
- Charlson comorbidity index (CCI)

Physical examination

Standard physical examination including body weight and height, with special attention for:

- Vital signs (Blood pressure, body temperature, pulse)
- WHO performance status (see appendix C)
- Palpable lymph nodes, spleen and liver sizes

Hematology

- Hemoglobin
- Leukocyte count
- Differential count
- Platelets count

At entry and on indication:

- DAT (direct antiglobulin test/Coombs test)
- PT
- PTT

Blood chemistry

- Creatinine clearance (calculated see appendix E)
- Bicarbonate
- Haptoglobin
- AST or ALT
- Bilirubine
- LDH

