10.5 Quality of Life assessment

Health related outcome parameters will be collected in this study, i.e. quality of life (QoL).

QoL will be assessed at entry, after 15 induction cycles and at 6 months, 1, 2 and 3 years after start maintenance/ observation.

The quality of life measurements will be continued after the patient is off protocol treatment, but discontinued when progression has been observed.

- EORTC QLQ-C30 questionnaire
- EORTC QLQ-CLL16

Collection of the QoL questionnaires will be performed in the following manner:

A QoL coordinator will be assigned in each participating center. The QoL questionnaire collection is left to the responsibility of the QoL coordinator. As soon as a patient is registered at the HOVON Data Center (HDC) the QoL coordinator is notified by email. Patient study number, (partial) date of birth and date of registration are mentioned in this mail.

The patient will be provided a paper print out of the questionnaire.

The baseline questionnaire will be handed or sent to the patient by the QoL coordinator. At the time points mentioned in the beginning of this section, the coordinator will hand over the questionnaire at the correct date.

The QoL coordinator will collect the questionnaire from the patient and will send them to the HOVON Data Center.

The questionnaires are described in appendix L.

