11.2 Follow up of patients withdrawn from protocol treatment

Patients who are withdrawn from treatment for other reasons than death will be followed as described in section 10.2 for follow up. SAE information will be collected as described in section 12.3.

However, for patients who are withdrawn from treatment because in hindsight they did not fulfill the eligibility criteria (see section 8.1) at time of enrolment, data will be collected until 30 days after the last protocol treatment given. SAE information will be collected as described in section 12.3

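### The visit schedule stops at progression after month 51 although all patients are to be followed for 7 years; if sites follow the schedule, late overall survival and time to next CLL treatment would be informatively censored

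*Protocol*

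**What the plan says.** **Schedule.** Section 10.1 lists 3- and 4-monthly evaluations after cycle 15, "whether in the maintenance or the treatment cessation group, until month 51 (15 months + 3 years"). No progression stop is attached to that period. The next line reads "Thereafter every 6 months until 7 years after registration or until progression, whatever comes first". Footnote 2 of Table 10.2.1, on the column for the period after month 51, says the same: "Every 6 months until 7 years after registration or until progression, whatever comes first".

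**Follow-up duration.** Section 10.1.1 has no exception: "All patients will be followed until 7 years after registration". The synopsis agrees: "Subsequently all patients will be followed until 7 years after registration".

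**Withdrawn patients.** Section 11.1 makes progression a reason for leaving protocol treatment. Section 11.2 then says "Patients who are withdrawn from treatment for other reasons than death will be followed as described in section 10.2 for follow up", which leads back to the table that carries the stop.

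**What depends on it.** Section 13.2 names OS and time to next CLL treatment as secondary endpoints. Section 14.4.4 places analysis VII, the update of the final analysis, when the last patient reaches 7 years.

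**Quality of life (QoL).** Section 10.5 has its own rule: questionnaires are "discontinued when progression has been observed". For restarted patients, note 2 of Table 10.2.3 says "Follow the original schedule: quality of life at 1, 2 and 3 years after start maintenance/observation".

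**The concern.** A site that works from the schedule would see no further visit for a patient who has progressed once month 51 has passed. A site that works from 10.1.1 would keep following that patient to year 7. The two readings give different data for the same endpoints.

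Death and the next line of treatment become more likely after progression. If contact ends there, the patients still at risk in the Kaplan-Meier estimate after month 51 are those who have not progressed, and their death rate stands in for everyone's. The OS estimate is then too high. Next treatments given after the last visit are also missed. An analysis plan cannot recover data that were never collected, so the point has to be settled in the protocol.

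The QoL conflict is separate. It concerns arm B patients who restart because of IWCLL progression: 10.5 would stop their questionnaires, while Table 10.2.3 keeps the original timetable.

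**Working it through.** **1. Does any other text supply the missing contact?**
- Table 10.2.1 has no row for survival status or subsequent treatment.
- Section 16.1 lists survival status as a CRF item, without a timetable.
- The registry follow-up in 10.1.1 is recommended, needs separate consent, and collects data after the end of the trial.
- Section 12.6 requires second malignancies to be reported to 5 years (month 60), or longer for patients still on maintenance, with no stop at progression. It covers neither survival nor next treatment.

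The all-patients statement in 10.1.1 and the synopsis is therefore the only text that requires this information to year 7, and the schedule contradicts it.

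**2. The plan's own design figures.** With 62 arm B patients and success at 44 or more, the exact binomial gives a one-sided error of 0.0492 at 60% and power of 0.812 at 75%. Then 62 × 3/2 = 93, 93/0.45 = 206.7 (207), and 230 × 0.90 = 207 (a 10% allowance is implied). All stated figures reproduce. The endpoint is read at month 27, before the stop can act, so none of them changes.

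**3. Size of the possible OS bias.** The protocol gives no rates for this, so these are assumptions: constant hazards per year, progression λ = 0.10, death before progression μ = 0.02, death after progression ν = 0.10 or 0.20. Months are counted from registration.

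Alive without progression at t years: P(t) = exp(−(λ+μ)t).
Alive after progression: Q(t) = λ·exp(−νt)·[exp((ν−λ−μ)t) − 1]/(ν−λ−μ).
True OS: S(t) = P(t) + Q(t).
If every progressed patient is lost at month 51 (4.25 years), or at progression if later, the only deaths observed afterwards occur at rate μ. The Kaplan-Meier estimate at 7 years tends to S(4.25)·exp(−2.75μ), where exp(−0.055) = 0.946.

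| | ν = 0.10 | ν = 0.20 |
|---|---|---|
| P(7) + Q(7) = true 7-year OS | 0.432 + 0.324 = 0.756 | 0.432 + 0.231 = 0.663 |
| P(4.25) + Q(4.25) = OS at month 51 | 0.600 + 0.266 = 0.867 | 0.600 + 0.216 = 0.817 |
| Estimate, all progressed patients lost | 0.867 × 0.946 = 0.820 | 0.817 × 0.946 = 0.773 |
| Overstatement | 6.4 points | 11.0 points |

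The values Q(4.25) mean that 22% to 27% of all patients would be alive, already progressed and off the schedule at month 51.

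**4. Partial loss.** If a fraction f of progressed patients is lost, the death rate seen after month 51 is [μP + ν(1−f)Q]/[P + (1−f)Q]. Integrating this from 4.25 to 7 years gives:
- f = 0.5: 0.780 and 0.706, an overstatement of 2.4 and 4.3 points.
- f = 0.2: 0.764 and 0.678, an overstatement of 0.8 and 1.5 points.
- f = 0: no bias.

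**5. Other assumed rates.** A simulation used 27-month PFS of 75% to 90%, death after progression of 0.01 to 0.04 per month and death without progression of 0.001 per month. With all progressed patients lost, the overstatement ran from about 5 points (0.840 true, 0.886 estimated) to about 18 (0.505 true, 0.688 estimated). The direction is constant as long as mortality is higher after progression.

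**The case against.** The strongest reply is that visits and follow-up are different things. Section 10.1 times clinical evaluations and Table 10.2.1 lists investigations, whereas 10.1.1 deals with follow-up and covers everyone. Survival status is on the CRF, and 11.2 cuts data collection short only for patients later found ineligible. On this reading, visits may end at progression while vital status is still collected. This stands in part: no text says that OS is censored at progression, so the bias is conditional on how sites act. It does not remove the contradiction, because 11.2 refers to 10.2 for follow-up and no timetable tells a site when to contact a progressed patient after month 51.

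Further limits also stand:
- No formal arm comparison is planned, and section 14.4.6 treats all but the primary analysis as hypothesis-generating.
- A reader might infer that survival is censored at progression from the start of the trial. The visits to month 51 carry no such stop.
- A reader might add time to treatment failure after restart to the affected endpoints. Table 10.2.3 gives restarted patients their own visits and response evaluations, so that endpoint is largely covered.
- A reader might blame the visit rule for missing QoL data. The last questionnaire is due 3 years after maintenance or observation starts, about month 51, and the stop at progression is an explicit choice in 10.5.
- The QoL conflict is narrow. Restart for MRD positivity is not progression, and under 13.1 neither is symptomatic CLL within 12 months that responds to restart in time. What remains unclear is later restart for IWCLL progression, or restart without response.

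**Conclusion.** The contradiction is real and should be resolved: 10.1 and footnote 2 of Table 10.2.1 against 10.1.1 and the synopsis, with 11.2 leaving it open. If sites follow the schedule, OS and time to next CLL treatment would be informatively censored between months 51 and 84. Under the main assumed rates, 7-year OS would be overstated by about 6 to 11 points with complete loss of progressed patients, and by about 1 to 4 points with a fifth to a half lost. These sizes rest on hazards that the protocol does not give. The bias is zero if 10.1.1 is followed.

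A reader might also infer a bias in the comparison of arm A, arm B and MRD-positive patients. That is plausible where progression rates differ, but it was not calculated and no formal comparison is planned. The primary endpoint and the sample size are not affected. The QoL inconsistency is a separate and smaller point.

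**What to change.** In section 10.1 and footnote 2 of Table 10.2.1, limit the progression stop to the disease-assessment visits. State that survival status and subsequent CLL treatment are collected every 6 months until 7 years after registration for all patients who still consent, by contact or record check after progression. Have 11.2 refer to this rule. Leave second malignancies on the timetable in 12.6.

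Separately, reconcile 10.5 with note 2 of Table 10.2.3 by stating whether arm B patients who restart because of IWCLL progression continue the questionnaires.

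The cost is amendment wording and a short 6-monthly status form for progressed patients, with no added procedures.

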10.1.1 Follow up

All patients will be followed until 7 years after registration.

To be able to collect long term follow up data until patient`s death after the end of this study, inclusion in a country specific registry (e.g. the Danish National CLL register or the Dutch Pharos registry or registry of the other Nordic countries) is strongly recommended. For this purpose, each patient will be informed about the importance of long term follow-up data and asked for his/her consent to the long term follow-up within an appropriate registry. For patients with a written informed consent for the registry, data for overall survival, late toxicities such as secondary malignancies, further treatments and the course of the disease will be collected after the end of the trial.

10.2 Required investigations

Table 10.2.1 Required investigations at entry, during treatment and during follow up

	At entry ¹	After each induction cycle	Extra at end of cycle 2	Cycle 3 day 8 and 15 Cycle 4 day1	Extra at end of cycle 3 and 6	Extra at end of cycle 9	Extra at end of cycle 12	Extra at day 15 of cycle 15 ⁹	After cycle 15: Every 3 months for 2 years, every 4 months for 3 rd year (= until 51 months)	Extra at month 27	After month 51 ²	Progressive disease
Informed consent	X											
Medical history	X											
Adverse events	X	X							X		X	
Physical examination	X	X							X		X	X
CIRS / CCI	X											
Rapid Report Form					X	X	X					
Binet stage	X											
TLS risk category (appendix G)	X		X ⁴									
Lab tests												
Hematology	X	X							X		X	X
Blood chemistry	X	X							X		X	
Additional chemistry	X											
Virology	X											
Bone marrow												
Bone marrow biopsy								X		X		X
(PET)-CT scan ⁵	X		X ⁶					X		X		X
(Clinical) response evaluation					X ⁷	X	X		X	X	X	X
Quality of Life ⁷	X								X ⁸		X ⁸	
Pregnancy test	X											

- Laboratory tests should be performed within 2 weeks prior to registration flow and CT can be maximally 42 days old
- Every 6 months until 7 years after registration or until progression, whatever comes first.
- The form needs to be filled out every 3 months for as long as the patient is on ibrutinib treatment
- In patients with high risk for TLS or CrCL 30-50 ml/min
- PET only in case of suspected transformation.
- CT scan after cycle 2 in patients with high risk for TLS or CrCL 30-50 ml/min
- Only at end of cycle 3
- Quality of life at entry, after induction cycle 15 and at 6 months, 1, 2 and 3 years after start maintenance/observation.

9. MRD and CT should be done at day 15 cycle 15 to have results available to assess SD, PR, CR, MRD negativity at end of cycle 15.

Table 10.2.2 .Collection for central lab.

	At entry	After each induction cycle	Extra at end of cycle 2	Cycle 3 day 8 and 15 Cycle 4 day1	Extra at end of cycle 3 and 6	Extra at end of cycle 9	Extra at end of cycle 12	Extra at day 15 of cycle 15 ⁴	After cycle 15: Every 3 months for 2 years, every 4 months for 3 rd year (= until 51 months)	Extra at month 27	After month 51	Progressive disease
Mutational status¹ PB	X											
Serum parameters	X											
FISH/CGH and NGS PB	X											X
MRD (flowcytometry)												
PB	X		X			X	X	X	X ²	X ²		X
BM aspirate								X		X		X
Side studies												
PB	X		X	X		X	X	X	X	X		X
BM aspirate								X		X		X
Lymph node biopsy												X ³

1 If not performed earlier

2 Patients becoming MRD pos. retest 1 month later (only during observation)

3 If accessible lymph node is present

4. MRD and CT should be done at day 15 cycle 15 to have results available to assess SD, PR, CR, MRD neg at end of cycle 15.

Table 10.2.3 Required investigations during/after reinitiation treatment¹

	Before start of reinduction treatment	Extra at end of cycle 3	Extra at end of cycle 12	After cycle 12: Every 3 months for 2 years, every 4 months for 3 rd year	Extra at 1 year after cycle 12	After month 51 ²	Progressive disease
Medical history	X			X		X	
Adverse events	X			X		X	
Physical examination	X			X		X	X
TLS risk category (appendix G)	X						
Lab tests							
Hematology	X			X		X	X
Blood chemistry	X			X		X	
Additional chemistry	X						
Bone marrow							
Bone marrow biopsy			X		X		
(PET)-CT scan	X		X		X		X
(Clinical) response evaluation		X	X		X	X	X
Quality of Life²	X						
CENTRAL LAB							
Flowcytometry PB (or BM if PB not done)							X
FISH/CGH and NGS PB							X
MRD (flowcytometry)							
PB			X	X	X		X
BM aspirate			X		X		X
Side studies							
PB			X		X		X
BM aspirate			X		X		X
Lymph node biopsy							X ³

1 Note that the required investigations from month 27 as mentioned in table 10.2.1 are required for all patients

2. Follow the original schedule: quality of life at 1, 2 and 3 years after start maintenance/observation

3. If accessible lymph node is present

Medical history

Standard medical history, including:

- B symptoms
- Concomitant diseases
- Concomitant medications
- Adverse events

At entry

- Proven CLL or SLL by minimal required markers (CD19/CD20/CD5/CD23/Kappa/Lambda)
- Cumulative Illness Rating Score (see appendix F)
- Binet classification (see appendix A)
- Charlson comorbidity index (CCI)

Physical examination

Standard physical examination including body weight and height, with special attention for:

- Vital signs (Blood pressure, body temperature, pulse)
- WHO performance status (see appendix C)
- Palpable lymph nodes, spleen and liver sizes

Hematology

- Hemoglobin
- Leukocyte count
- Differential count
- Platelets count

At entry and on indication:

- DAT (direct antiglobulin test/Coombs test)
- PT
- PTT

Blood chemistry

- Creatinine clearance (calculated see appendix E)
- Bicarbonate
- Haptoglobin
- AST or ALT
- Bilirubine
- LDH

Special attention to tumor lysis lab according to appendix G. Please see appendix G for full details.

Additional blood chemistry at entry

- Glucose
- Total protein
- Albumin
- IgG
- IgM
- IgA
- Monoclonal protein
- β -2 microglobulin

Virology

- Hepatitis B surface antigen (HBsAg) and hepatitis B core antibody (anti-HBc).
- Hepatitis C virus (HCV), if positive: HCV- (RNA)
- Human immunodeficiency virus (HIV) positive patients;

Bone marrow examination . Bone marrow pathology will be performed locally. Side studies will be performed centrally by bone marrow aspirate.

(PET-)CT scan

A (high resolution PET-)CT scan of neck, thorax, abdomen and pelvis and reported according to Cheson criteria. CT scan to determine lymphnode size(s) is obligatory to evaluate CR.

